## **Study Design and Procedures**

This will be a single-blinded comparative effectiveness randomized controlled trial conducted in a real-world setting. Subjects with HF and their caregivers (dyads) will be recruited and randomly assigned to one of two study arms:

- a provider-directed management model (with home monitoring equipment), a standard care-plus, OR
- an enhanced-mHealth care management model (with connected monitoring equipment).

Both groups will receive HF guideline-directed usual care, defined by the American Heart Association and College of Cardiology HF Guidelines with widely demonstrated effectiveness and have the same opportunity for education, nutrition counseling, nurse management, and HC provider access. This is usual care at UAMS.

Recruitment: Research participants will be recruited consecutively from the UAMS Medical Center. The project director will receive a daily list from UAMS bioinformatics core via UAMS secure/encrypted email of patients admitted to the hospital with a primary or secondary diagnosis of heart failure. Patients will be visited by the research team when they are stable and likely the day of discharge from the hospital (that way, likely the family/caregiver will be here as well). At that time, information will be given to the patient (and family/caregiver if present) about the study. If they would like to, we will obtain consent from both the patient and the caregiver if agreeable. Alternatively, they can think and talk about whether they want to participate and we will follow up after return home.

See section on participants and human subject protection for more details on

Study Title: Innovative Care of Older Adults with Chronic Heart Failure (I-COACH): A Comparative Effectiveness Clinical Trial  
PI (researcher): [name], RD  
Institution: University of Arkansas for Medical Sciences  
Funding: PCORI Grant

recruitment & consent.

The randomization will be generated using a computer algorithm using random permuted blocks (of differing size) to ensure balance over time in the numbers allocated to intervention groups and to avoid study staff anticipating the next treatment allocation. Randomization will be centrally generated by Co-I [name] and study staff who allocate interventions will be blinded to both the sequence and size of the blocks.

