Participants will be randomized then they will complete baseline measures (self-reported survey measures, see Table 1.). Because all participants & caregivers will participate in the same recruitment procedures, measure timelines, and will receive monitoring equipment, participants will be blinded to their assigned group and will not be informed of which is the active intervention group. Both groups will receive standard education provided by the hospital and clinic providers, in addition the study staff will emphasize portions of the standard education provided regarding *emergency situations that require immediate action from the patient and/or caregiver such as; hypertension crisis, stroke signs and symptoms, and signs and symptoms of heart attack.*

**The provider-directed management model** is the current standard of care in the treatment of patients with HF including guideline-based HF care and a fee-for-service payment model in which the number of services and procedures that are provided are billed. Patients are typically scheduled for provider visits at a periodic interval rather than on patient needs, preferences, or circumstances. Care delivery is based on convenience of provider and sometimes on priority-based queues, that is If patients are having problems, they typically call the providers office or set up an appointment to visit the clinic weekdays and get priority scheduled. If problems occur at a different time, they frequently go to the emergency department (ED) at a local hospital or UAMS.

Caregiver burden is substantial in this model considering the patients' problem solving, care, and transportation needs. Our previous research confirmed both the traditional call/wait approach and ED alternative as usual means of provider communications. However, in this study, we are supplementing standard care by providing and training each patient in the use of an analog kit: (not internet connected) weight scale, blood pressure cuff, pulse oximeter, and a Log for recording their vital sign measures. Patients will be trained on the equipment and told to obtain a reading of weight, BP, and POx saturation every morning when they arise. Participants will make appointments, receive consultations, case-management, and resolve problems through in-person appointments or telephone communications as usually scheduled during the 6-month study follow-up.

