Study Title: Innovative Care of Older Adults with Chronic Heart Failure (I-COACH): A Comparative Effectiveness Clinical Trial

PI (researcher): [name], RD

Institution: University of Arkansas for Medical Sciences

Funding: PCORI Grant

Subjects will be instructed to record their daily readings on a paper log provided by the research team. These monitoring devices will not transmit readings to a centralized

location and no one will be alerted to out-of-range readings or compliance with taking daily vital sign measures. At the front page of the log, normal ranges will be described with brief instructions about what participants/caregivers should do if their readings are out-of-range. These instructions will be developed with guidance from physicians/providers in the cardiology department. Per protocol, participants will be instructed to telephone the provider's office or the standard "on-call" line for further consultation and evaluation as needed. The number of provider visits will be collected using the electronic medical record and patient self-report). Patients will be encouraged to bring their vital sign measure logs to their provider appointments. Logs will be collected at the completion of their participation in the study. The log data will be recorded and saved for further data analysis.

**The mHealth care management model.** We will provide each patient randomized to this group with a weight scale, blood pressure cuff, & pulse oximeter (POx) kit connected to a Bluetooth-paired Android Health Tablet over the 6 months. This will allow real-time collection and monitoring of patient's vital sign measures, instantly accessible 24 hours a day, every day, by both patients and their clinicians, via a wireless gateway that transmits readings to a secure cloud-based clinician portal. The clinician portal will be monitored by the hospital's call center where registered nurses (RNs) will be specially trained to triage these patients according to physician/provider and study team-developed protocols.

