Patients will be trained on the equipment and obtain a reading of weight, BP, and symptom survey every morning when they arise. A POx saturation reading will be obtained as needed. We used identical procedures in our pilot study and reported high patient daily adherence (85%) and call center accuracy (90%). Patients have the option to receive patient-centered education, nutrition counseling, nurse & medication management, and problem-based medical visits through live audio and video connected technology in their home. Diagnostic testing and some problems, if needed, will necessitate a visit to a local laboratory, regional UAMS clinic or main campus as usual. Caregivers will be encouraged to attend sessions or telehealth appointments from any location virtually. We will work with the providers, case managers, and our hospital system to train for telehealth visits as well as coding and billing.

Vital sign readings will be sent to the secure cloud-based software. Patients will be encouraged to take their vital signs daily. If the readings are out-of-range, the Registered Nurse (RN) Call Center will be automatically alerted via an email message. Protocols were developed by the medical providers as to acceptable and unacceptable

Study Title: Innovative Care of Older Adults with Chronic Heart Failure (I-COACH): A Comparative Effectiveness Clinical Trial  
PI (researcher): [name], RD  
Institution: University of Arkansas for Medical Sciences  
Funding: PCORI Grant

vital sign ranges/readings and actions. (We did this with the pilot study, and the procedure worked well). If within normal range, no intervention would be needed, and readings will be saved for future data analysis. This is considered a “green light”, that is no alert is triggered and no intervention is needed.

If readings are missed or trending out of range, or out of range now, the call center RN will follow the provider/study team developed protocol or algorithm for “yellow light” “orange light” or “red light”, in order of severity. The call center will monitor patients Monday-Friday 7-4pm as per the provider developed protocol. Patients will be instructed on what to do outside of those hours.

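### The arms are visibly different, so participants cannot be blinded to their assigned group as stated, and the single-blind label overstates protection of the self-reported primary outcome

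*Combined protocol and SAP*

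**What the plan says.** Study Design and Procedures opens with the label: "This will be a single-blinded comparative effectiveness randomized controlled trial conducted in a real-world setting". After the randomization paragraph it says who is blinded: "participants will be blinded to their assigned group and will not be informed of which is the active intervention group". The reason given is that everyone shares the recruitment procedures and measurement timelines and receives monitoring equipment.

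The same section then describes the two arms.

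- **Provider-directed arm.** Each patient gets "an analog kit: (not internet connected) weight scale, blood pressure cuff, pulse oximeter, and a Log for recording their vital sign measures". Nothing is transmitted, and "no one will be alerted to out-of-range readings or compliance with taking daily vital sign measures".
- **mHealth arm.** Each patient gets a kit "connected to a Bluetooth-paired Android Health Tablet over the 6 months". There is a symptom survey every morning, call-center nurses telephone when alerts require it, and education, counseling and problem-based visits are available "through live audio and video connected technology in their home". Patients are told that they may contact the call-center nurse by tablet or telephone. Caregivers may be called if the patient does not answer.

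The only other blinding statement concerns randomization: "study staff who allocate interventions will be blinded to both the sequence and size of the blocks".

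Table 1 names the Self-Care of HF Index as the primary outcome, and Data Analysis specifies its management subscale. Table 1 takes hospital visits, emergency visits, provider visits and mortality from the medical record. The provider-directed section adds that provider visits also draw on patient self-report.

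**The concern.** The blinding sentence makes two claims. One is that participants are not told which arm is the active one, which is feasible. The other is that they are blinded to their assigned group, which the arm descriptions contradict. Giving equipment to everyone does not mask the assignment when the equipment, the monitoring and the human contact all differ.

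This matters because the primary outcome is the patient's own rating of self-care. A patient who knows that a nurse is watching the readings, or that nobody is, may rate self-care differently for reasons other than a change in self-care. Part of the effect of being monitored is the intervention itself, so not every such difference is bias. The design cannot separate the two, however, and a report that calls the trial single-blind would tell readers that this source of bias had been controlled.

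**Working it through.** No figure in the plan needs reproducing here, so the check sets the text side by side.

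**1. Could a participant be unaware of the assigned service?**

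| Feature | Provider-directed arm | mHealth arm |
|---|---|---|
| Devices | Unconnected scale, cuff and oximeter | Bluetooth scale, cuff and oximeter with a tablet |
| Recording | Paper log kept by the patient | Automatic transmission to a clinician portal |
| Daily symptom survey | Not described | Every morning |
| Response to abnormal or missed readings | Nobody alerted; patient telephones the office or on-call line | Call-center nurse follows up under a graded alert protocol |
| Visits | In person or by telephone as usual | Optional live video at home as well |
| Caregiver contact by call center | Not described | Called if the patient does not answer |

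Each row is something that the patient, and in the last row the caregiver, experiences directly. Neither can be unaware of the service received. What can be withheld is which service the trial expects to do better.

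**2. Does any other blinding support the label?** Staff who allocate are blinded to block sequence and size. That stops them from predicting the next assignment, which is allocation concealment. It ends once the assignment is made and says nothing about who collects or analyses outcomes. Outcome Measures and Measurement Procedures gives the Research Assistant role both completion of measures and equipment training. The Language section allows instruments to be read aloud. Someone who knows the arm may therefore be present when answers are given. Data Handling and Recordkeeping describes a coded, de-identified dataset, but coding identities does not mask the arm.

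**3. Which outcomes are exposed?**

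- *Exposed:* the primary outcome, and self-ratings by patients (for example confidence, self-efficacy, health distress, quality of life and satisfaction) and by caregivers (burden and health).
- *Probably less exposed:* the HF knowledge scale, since it tests knowledge.
- *Not protectable by masking:* the usability scale, which rates technology that differs between arms by design.
- *Less exposed:* admissions, emergency visits and mortality counted from the record. Provider visits fall in between, because self-report contributes to them.

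**4. How large is the bias?** It cannot be computed. The documents give no reporting-bias figure, no outcome standard deviation and no power calculation. The conclusion does not depend on a number.

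**The case against.** The strongest reply is that comparisons of care models in routine practice cannot mask the service received, that the protocol describes the arm differences openly, and that single-blind here means only that participants are not told which arm is active. Much of this stands. Nobody could make these arms indistinguishable, the point does not ask for that, and the main remedy changes words more than data. The reply does not rescue the text, though, because the sentence claims blinding to assigned group in addition to withholding which arm is active.

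Several stronger readings are tempting but not supported.

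- **That no one is masked anywhere in the plan.** Title and consent pages are removed, the Appendices heading has no content beneath it, and the Data Management Plan is a separate document still to be developed. Only the available text can be said to describe no masking of collectors or analysts.
- **That the same person trains and assesses a given participant.** The protocol gives both tasks to the Research Assistant role and does not say that one person does both.
- **That baseline adjustment fails because baseline follows randomization.** The protocol does say "Participants will be randomized then they will complete baseline measures". It does not say that participants know their arm or hold the equipment by then. Nor would a pre-randomization baseline remove a reporting shift that arises during follow-up. Baseline timing is a separate matter.
- **That questionnaire mode differs by arm.** The Language section mentions loading instruments on a tablet, and the only tablet otherwise described is the mHealth one. That tablet is not identified, however, and both groups are offered take-home forms and the same home, telephone and clinic options. A difference is possible but not shown.
- **That the share of self-reported rows in Table 1 measures exposure.** It depends on table layout: one row combines several record-based outcomes, and one Promis row covers seven domains.

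**Conclusion.** The stated blinding of participants to their assigned group is wrong as written, because the arm descriptions in the same section rule it out. Participants and caregivers are unmasked to the care model and at most unaware of the hypothesis. Nothing else in the available text supplies masking of outcome assessment or analysis. The label therefore overstates how well the self-reported outcomes, including the primary, are protected.

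The size and direction of any reporting bias are unknown. A reader might infer that the primary comparison is biased in favor of mHealth, but the documents do not show that. The conclusion rests on the arm descriptions being delivered as written and on the removed pages not describing masking of collectors or analysts. If they do, that part falls and the point about participants remains.

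**What to change.** 1. Replace both blinding phrases with wording such as: *participants and caregivers are not masked to the care model received; they are not told which arm is hypothesised to be better*. State with the interpretation that self-reported outcomes, including the primary, are open to reporting bias, and that admissions, emergency visits and mortality counted from the record are less so.
2. State that outcome collectors are unmasked, unless they are in fact masked. Have analysts run the primary analysis on coded arm labels where feasible.
3. As a low-cost precaution, and not because a fault has been shown, offer the same questionnaire modes in both arms, not tied to the mHealth tablet, and record the mode used. If the Data Management Plan already covers this, a cross-reference is enough.

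The cost is protocol wording, coding of arm labels for the analyst, one added data field and loss of the blinded label. Arms, endpoints and sample size do not change.

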### **Outcome Measures and Measurement Procedures**

Measurement instruments are included in Table 1 (next page) and grouped for the patient, caregiver, and system measures, specific aim addressed and type of outcome measure.

After screening to determine eligibility and fully informed consent process is followed and obtained, participants and caregivers will be randomized and asked to complete baseline assessments. Participants in both groups will be allowed to take assessment

Study Title: Innovative Care of Older Adults with Chronic Heart Failure (I-COACH): A Comparative Effectiveness Clinical Trial  
PI (researcher): [name], RD  
Institution: University of Arkansas for Medical Sciences  
Funding: PCORI Grant

questionnaires home to fill out within 1 week (+/- 1 week). The Research Assistant (RA) will travel to the participants' home, will be available by phone, or will arrange a convenient time before or after a closely timed provider appointment to complete the measures and train on use of the equipment. We will offer these convenience techniques at baseline, 3- and for the final 6-month follow-up measures.

### **Compensation**

Participants and Caregivers will receive compensation for each measurement interval to thank them for their time and to encourage completion of the study. Participant incentives will be \$25 each for baseline and 3-month measures, and \$50 for the final 6-month measure (for a total of \$100). Caregiver compensations are \$25 each at baseline and at 6-months (total \$50). Participants and Caregivers will also be reimbursed for gas mileage expense (\$.58 per mile per PCORI standards).

### **Language**

Instruments will be provided for English and Spanish-speaking patients, may be read to the participants if desired, and will be installed with large print and/or an easy-to-use format loaded on the tablet device. Outcome data/measures for the provider and hospital system will be obtained from the electronic medical record and hospital computer database within 30 days after the 6-month follow-up measures have been completed.

Study Title: Innovative Care of Older Adults with Chronic Heart Failure (I-COACH): A Comparative Effectiveness Clinical Trial  
 PI (researcher): [name], RD  
 Institution: University of Arkansas for Medical Sciences  
 Funding: PCORI Grant

**Table 1. Specific Aim Addressed, Measure, Outcome Type, Purpose of Measure, Administration Interval & Estimated Participant Completion Time**

SP. AIM	Measure	Outcomes	Purpose of Measure	Base line	3 mth	6 mth	Completion Time
PATIENT CENTERED OUTCOME MEASURES							
1a	Self-Care of HF Index v7.2	Primary Outcome:	Assess self-care management, symptom perception & maintenance skills	X	X	X	8 min.
3	Self-Care Confidence 	Hypothesized Mediator:	Assess confidence in ability to care for self	X	X	X	3-5 min.
3	Promis® Self-Efficacy to Manage Symptoms 	Hypothesized Mediator:	Assess ability to manage symptoms for chronic conditions	X	X	X	15-20 min.
3	Promis® Self-Efficacy to Manage Medications & Treatments 	Hypothesized Mediator:	Assess ability to manage medication & treatments for chronic conditions	X	X	X	20 min.
3	Dutch HF Knowledge Scale 	Hypothesized Mediator	Assess Knowledge of HF	X	X	X	5 min
1a & 2	Promis® 43v2.1 Health profile 	Secondary Outcome Patient Characteristics	Assess physical function, anxiety, depression, fatigue, sleep, social roles, and pain	X	X	X	10-20 min.
1a	Health Distress 	Secondary Outcome Patient Characteristics	Assess psychological impact/health distress	X	X	X	1-3 min
1a	Promis® Informational Support v 2.0 6a 	Secondary Outcome	Assess perceived availability of helpful information or advice	X	X	X	2-4 min.
1a	System Usability Scale 	Secondary Outcome	Ease of using the technology		X	X	3-5 min.
2	St. Louis University Mental Status (SLUMS) Examination 	Secondary Outcome: Patient Characteristic	Cognitive assessment (OBJECTIVE MEASURE)	X			10 min.
2	Patient Demographics (self-report & medical record review)	Secondary Outcome: Patient Characteristics:	Education, income, rurality, HF severity, years diagnosed, caregiver location, etc	X			5 min.
1a	Minnesota Living with HF (MLHFQ) 	Secondary & Long-Term Outcome	Assesses Quality of Life	X		X	5-10 min.
2	Newest Vital Sign 	Secondary Outcome: Patient Characteristics	Screens for Health Literacy	X			5 min.
CAREGIVER CENTERED OUTCOME MEASURES							
1b	Caregiver Burden 	Secondary Outcome	Assess caregiver perception of burden	X		X	30 min.
1b	Optum®SF-36® v2 Health Survey 	Secondary Outcome	Health domains- Functional Psych. Health & Well-being	X		X	5-10 min
PROVIDER & HEALTH SYSTEM MEASURES							
1c	Satisfaction with Care 	Secondary Outcome	Patient assesses satisfaction with care	X	X	X	1-3 min
1c & 2	Hospital, Emergency Visits, Provider Visits, Mortality	Secondary Outcome	Counts from Medical Record	X	X	X	N/A

Study Title: Innovative Care of Older Adults with Chronic Heart Failure (I-COACH): A Comparative Effectiveness Clinical Trial  
PI (researcher): [name], RD  
Institution: University of Arkansas for Medical Sciences  
Funding: PCORI Grant

